### **6.3.3 Observed Case Analysis**

Missing values will not be used for the observed case analysis.

### **6.3.4                    Imputation of Missing Dates**

For baseline, efficacy, and safety parameters, if the day and/or month are missing, the following conventions will be used to impute the missing dates:

- 01 for missing start day
- End of month for missing end day
- January 1 for missing start month
- December 31 for missing end month

## **7.0                    Demographics, Baseline Characteristics, Medical History, and Previous/Concomitant Medications**

The subsequently described analyses will be provided by active uveitis (defined as having discontinued the parent study, Study M10-877/M10-880 due to Treatment Failure) versus inactive uveitis and overall in the ITT set.

All statistical analyses will be descriptive. Descriptive statistics will include the number of observations, mean, standard deviation, minimum, first quartile, median, third quartile, and maximum for continuous variables; and counts and percentages for discrete variables.

### **7.1                    Demographic and Baseline Characteristics**

Variables to be summarized at baseline of Study M11-327 will include:

- **Subject demographics**
  - Age (years)
  - Age categories 1 (< 40, 40 – 64, ≥ 65 years)
  - Age categories 2 (< 30, ≥ 30 to < 50, ≥ 50 years)
  - Gender (male/female)
  - Race (white, black, Asian, American Indian/Alaska native, native Hawaiian or other Pacific islander, other)
  - Ethnicity (Hispanic or Latino, no ethnicity)

- Asian race (Chinese, Japanese, Korean, Taiwanese, Singaporean, Malaysian, other) (only for subjects from Japan)
- **TB history/PPD test/QuantiFERON®-TB Gold test/TB prophylaxis**
  - BCG vaccination (yes, no)
  - Induration of Tuberculin PPD skin test (mm)
  - Tuberculin PPD skin test (negative, positive), positive defined as  $\geq 5\text{mm}$
  - QuantiFERON-TB Gold test (negative, positive, indeterminate)
  - Combined result of Tuberculin PPD skin test and QuantiFERON-TB Gold test
  - Enrollment under TB prophylaxis (yes, no)
- **Chest x-ray (only in subjects with positive TB test)**
  - Chest x-ray findings (normal, abnormal)
  - Calcified granulomas (absent, present)
  - Pleural scarring (absent, present)
  - Pleural thickening (absent, present)
  - Findings indicative of previous TB infection (yes, no)
- **Vital signs**
  - Systolic blood pressure (mmHg)
  - Diastolic blood pressure (mmHg)
  - Pulse (bpm)
  - Respiratory rate (rpm)
  - Temperature ( $^{\circ}\text{C}$ )
- **Patient reported outcomes**
  - Visual Functioning Questionnaire (VFQ-25): total score and subscale scores
  - EuroQol-5D Questionnaire (EQ-5D)
  - Work Productivity and Activity Impairment: Specific Health Problem Questionnaire (WPAI:SHP) and its components

The following **ophthalmologic variables** will be summarized separately for left and right eye at baseline of Study M11-327:

- Optical coherence tomography (OCT) evidence of macular edema (yes, no)
- Central retinal thickness (microns)
- Intraocular pressure (mmHg)
- Active chorioretinal lesions (yes, no) via dilated indirect ophthalmoscopy (DIO)
- Active retinal vascular lesions (yes, no) via DIO
- Anterior chamber (AC) cell grade (SUN criteria) (continuous and categorical)
- AREDS lens opacity grading (no statistical test):
  - nuclear opacity (grade < 1.0, 1.0, 1.5, 2.0, 2.5, 3.0, > 3.0)
  - cortical opacity (grade < 1.0, 1.0, 1.5, 2.0, 2.5, 3.0, > 3.0)
  - posterior subcapsular opacity (grade < 1.0, 1.0, 1.5, 2.0, 2.5, 3.0, > 3.0)
- Vitreous haze grades (NEI/SUN criteria) (continuous and categorical)
- LogMAR Best corrected visual acuity (BCVA) will be calculated as follows:
  - if  $\geq$  20 letters were read at 4 m OR if < 20 letters were read at 4 m but the test was not done at 1 m,  
$$\text{logMAR} = 1.7 - 0.02 * (\text{number of letters read at 4 m} + 30),$$
  - if < 20 letters were read at 4 m and the test was also done at 1 m,  
$$\text{logMAR} = 1.7 - 0.02 * (\text{number of letters read at 4 m} + \text{number of letters read at 1 m})$$
  - if 0 letters were read at 1 m, the following logMAR values will be calculated according to Holladay (1997):
    - in case of finger counting:  
$$\text{logMAR} = (-1) * \log_{10}(\text{distance in meters}/60)$$
    - in case of hand movements:  $\text{logMAR} = 3.0$
- Power of sphere (diopters)
- Power of cylinder (diopters)
- Axis of cylinder (degrees)

For analysis of central retinal thickness, the central retinal thickness measured by the investigator will be used. Central retinal thickness will be analyzed by OCT machine. Central retinal thickness and macular edema will be analyzed excluding patients with macular hole and/or rhegmatogenous retinal detachment affecting the macular. OCT evidence of macular edema will be defined as center point thickness  $\geq$  260 microns for Stratus,  $\geq$  320 microns for Cirrus,  $\geq$  340 microns for Spectralis.

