Likewise, in a Spanish prospective, uncontrolled study of 19 adult subjects with bilateral chronic non-infectious uveitis (1 anterior, 3 intermediate, 5 posterior and 10 panuveitis) or refractory uveitis who have failed or were intolerant to corticosteroid and immunosuppressive therapy, patients were treated with adalimumab 40 mg every other week (eow) subcutaneously for 1 year.²³ Twelve (63%) subjects achieved control of intraocular inflammation at the end of the follow-up period. All subjects were able to decrease concomitant immunosuppressives by at least 50%. Of the 33 eyes with CME at study start, 55% had complete resolution at Month 12. There was also statistically significant improvement in the mean visual acuity, anterior chamber (AC) and vitreous cavity inflammation. Only minor local adverse effects were noted.

Díaz-Llopis et al published in 2012 a prospective study on 131 subjects treated with adalimumab 40 mg eow and followed for 6 months. Anterior chamber inflammation and vitreous inflammation decreased significantly (P 0.001) from a mean of 1.51 and 1.03 at baseline to 0.25 and 0.14, respectively, at 6 months. Macular thickness was 296 (102) at baseline versus 240 (36) at the 6-month visit (P 0.001). Visual acuity improved by 0.3 logMAR in 32 of 150 eyes (21.3%) and worsened by 0.3 logMAR (15 letters) in 5 eyes (3.3%). The dose of corticosteroids decreased from 0.74 (3.50) to 0.20 (0.57) mg/kg/day (P 0.001). Cystoid macular edema, which was present in 40 eyes at baseline, showed complete resolution in 28 (70%) eyes at 6 months.

One hundred eleven (111) patients (85%) were able to reduce at least 50% of their baseline immunosuppression load.

Nine (9) patients (6.9%) had severe relapses during the 6 months of follow-up.⁴¹

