### **10.2 Efficacy Variables**

The following efficacy variables will be analyzed:

- Proportion of subjects with no active lesions in both eyes at each study time point.
- Proportion of subjects at each study time point with no new active, inflammatory chorioretinal or inflammatory retinal vascular lesion in both eyes relative to Baseline for subjects who had inactive uveitis when they entered the study and to Week 8 for subjects who had active uveitis when they entered the study.
- AC cell grade left/right eye and mean of both eyes at each study time point.
- Proportion of subjects at each study time point with a Grade  $\leq 0.5+$  in AC cells in both eyes on Slit Lamp Exam, according to SUN criteria.

- VH grades left/right eye and mean of both eyes at each study time point.
- Proportion of subjects at each study time point with a Grade  $\leq 0.5+$  in vitreous haze in both eyes on indirect ophthalmoscopy, according to NEI/SUN criteria.
- Proportion of subjects at each study time point with VH  $\leq 0.5$  and AC  $\leq 0.5$ .
- Proportion of subjects at each study time point with new lesions, AC  $\geq 2$  or VH  $\geq 2$ .
- Proportion of subjects at each study time point in quiescence defined as no active lesions, AC  $\leq 0.5$  and VH  $\leq 0.5$ .
- Proportion of subjects who experienced a uveitis flare (defined as no quiescence) during the study and who did or did not discontinue from the study due to the flare.
- LogMAR Best corrected visual acuity (BCVA) left/right eye and mean of both eyes at each study time point.
- Proportion of subjects at each study time point without a worsening of BCVA by  $\geq 15$  letters on the Early Treatment Diabetic Retinopathy Study (ETDRS) in both eyes relative to Baseline for subjects who had inactive uveitis when they entered the study and to Week 8 for subjects who had active uveitis when they entered the study.
- Proportion of subjects who started IMMs in Study M11-327.
- Proportion of subjects on/off IMMs at each study time point only in subjects on IMMs at baseline of Study M11-327.
- Proportion of subjects at each study time point achieving a  $\geq 50\%$  reduction in immunosuppression load relative to Baseline for subjects who had inactive uveitis when they entered the study and to Week 8 for subjects who had active uveitis when they entered the study.

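### The SAP's logMAR rule credits 30 untested letters to an eye reading fewer than 20 letters at 4 m with no 1 m test, which can understate poor vision and distort the 15-letter endpoint in either direction

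*SAP*

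**What the plan says.** SAP Section 7.1 gives the only logMAR formula in the plan, and it has three branches.

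- An eye reading at least 20 letters at 4 m scores 1.7 − 0.02 × (4 m letters + 30). The same formula applies when fewer than 20 "letters were read at 4 m but the test was not done at 1 m".
- When fewer than 20 "letters were read at 4 m and the test was also done at 1 m", only the letters actually read at 1 m are added to the 4 m count.
- Vision off the chart has its own values, but under a condition: "if 0 letters were read at 1 m, the following logMAR values will be calculated". Finger counting is then converted from the distance, and hand movements are set to 3.0.

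Section 7.1 concerns the baseline summary. Section 10.2 then lists "LogMAR Best corrected visual acuity (BCVA) left/right eye and mean of both eyes at each study time point" as an efficacy variable and gives no other formula. Section 10.2 also lists the proportion of subjects "without a worsening of BCVA by" at least 15 "letters on the Early Treatment Diabetic Retinopathy Study (ETDRS) in both eyes relative to Baseline", or relative to Week 8 for subjects who entered with active disease. It does not say how the letter score is built.

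SAP Section 6.3.1 treats missing binary outcomes as non-response. Section 6.3.2 carries the last value forward for continuous variables. Protocol Section 5.3.1.1 leaves the conduct of acuity testing to a Visual Acuity Manual that is not among the documents.

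**The concern.** For an eye that reads well at 4 m, adding 30 letters stands in for a 1 m chart it could be expected to read in full. For an eye that reads fewer than 20 letters at 4 m, that expectation is weakest, yet the plan grants the same credit when nothing was measured at 1 m. At a given 4 m count, an untested eye can therefore never score worse than a tested one.

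The usual safeguards do not catch this. The rule returns a number, so the visit is not missing. Non-responder imputation does not apply, the observed-case analysis includes the value, and LOCF can carry it forward. Mean logMAR, its confidence interval and graph, the Section 10.4 subgroup results and possibly the 15-letter endpoint all depend on it. The SAP plans no sensitivity analysis for it.

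**Working it through.** **Inputs.** The formulas come from SAP Section 7.1. The conversion of 15 letters to 0.3 logMAR (0.02 per letter) appears in Protocol Section 3.5.2. The 1 m maximum is not stated. I assume 30 because the credit is 30 and because moving from 4 m to 1 m is worth log10(4)/0.02 = 30.1 letters. Write F4 for letters at 4 m and N1 for letters at 1 m, with N1 running from 0 to 30.

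**Score at a single visit.** Without a 1 m test, logMAR = 1.7 − 0.02 × (F4 + 30). With the test, logMAR = 1.7 − 0.02 × (F4 + N1). The gap is 0.02 × (30 − N1), that is 0 to 0.60 logMAR or 0 to 30 letters.

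| F4 | Score with no 1 m test | Score if tested, N1 = 30 to 0 |
|---|---|---|
| 0 | 1.7 − 0.02 × 30 = 1.10 | 1.10 to 1.70 |
| 10 | 1.7 − 0.02 × 40 = 0.90 | 0.90 to 1.50 |
| 19 | 1.7 − 0.02 × 49 = 0.72 | 0.72 to 1.32 |

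The rule always sits at the best end of the range. Read literally, the off-chart values need a 1 m result of 0 letters, so an eye never tested at 1 m cannot score worse than 1.10. Finger counting at 1 m would be −log10(1/60) = 1.78, which is 0.68 worse. Hand movements would be 3.0, which is 1.90 worse.

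**Masked loss (1 m test missing at follow-up).** This step assumes that the Section 7.1 scoring is also used for the 15-letter endpoint. Let R4 be the 4 m count at the reference visit.

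- For R4 ≥ 20 the reference score is R4 + 30. The apparent loss is R4 − F4 and the true loss is R4 + 30 − F4 − N1.
- A loss escapes only if R4 − F4 ≤ 14. Since F4 ≤ 19, this needs R4 ≤ 33. The exposed range is R4 = 20 to 33, a total score of 50 to 63, or logMAR 0.70 to 0.44.
- Masked: R4 = 20 (score 50, logMAR 0.70) and F4 = 6 untested (score 36, logMAR 0.98) give an apparent loss of 14, not counted. If N1 is really 15, the score is 21 (logMAR 1.28) and the true loss is 29.
- Not masked: R4 = 40 (score 70) and F4 = 6 untested (score 36) give an apparent loss of 34, counted. The true loss is 49 if N1 = 15, so only the size is wrong.
- An eye below 20 letters at 4 m at reference, but tested at 1 m, can also be masked. Take 10 + 30 = 40 letters at reference and 0 at 4 m untested at follow-up (score 30). The apparent loss is 10 and the true loss is between 10 and 40.

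**False loss (1 m test missing at the reference visit).** Take a stable eye with 5 letters at 4 m and 15 at 1 m. Untested at reference, it scores 35. Tested later, it scores 20. The apparent loss is 15 letters with no change in vision. With 10 letters at 1 m the false loss is 20.

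**The case against.** The strongest reply has four parts.

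- **Direction and reach.** A reader might infer that the error always flatters the drug and that losses of vision are hidden in general. The arithmetic does not support either inference. The score at the affected visit is always favourable, but the change is not: a missing 1 m test at the reference visit can manufacture a loss. Among eyes reading at least 20 letters at 4 m at reference, masking of the binary endpoint is confined to counts of 20 to 33. An eye falling from 40 letters at 4 m to 0 scores 70 and then 30, a 40-letter loss, and is counted as worsened. Stable eyes with long-standing poor vision fall under the same rule as eyes that have declined. This part stands.
- **The letter endpoint.** Section 10.2 states no scoring for it, so the carry-over from Section 7.1 is an inference. That stands too, though the absence of a stated rule is itself a gap.
- **Frequency.** The documents do not say when a 1 m test must be done or how often it is omitted, so a reader should not infer that its absence is a breach of procedure or that it is common. This stands.
- **Remedy.** Setting such values to missing looks tidy but can be worse for logMAR. Suppose an eye read 40 letters at 4 m at the previous visit (0.30) and now reads 0 with no 1 m test. The present rule gives 1.10, whereas missing plus LOCF gives 0.30 and removes the whole decline. In the observed-case mean the poor eye would disappear. This stands and shapes the fix below.

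Efficacy is descriptive and the primary objective is safety, so no test depends on this. That limits the weight of the point, but it does not justify counting unmeasured letters as read.

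**Conclusion.** The point holds in a limited form. Section 7.1 assigns an untested poor eye its best possible score, and the visit can be understated by 0 to 30 letters (0 to 0.60 logMAR), or more where vision is off the chart. The upper end is twice the 15-letter threshold.

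For the 15-letter endpoint the effect is conditional. A true loss can be masked when the follow-up visit lacks the 1 m test, and a false loss can appear when the reference visit lacks it. The conclusion rests on two assumptions: a 1 m maximum of 30 letters, and use of the Section 7.1 formula after baseline and for the letter endpoint. The SAP offers no alternative to that formula. The number of eyes involved, and therefore the net effect on any reported figure, cannot be determined from the documents.

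**What to change.** 1. State in SAP Section 10.2 how the ETDRS letter score is calculated, and do not count untested 1 m letters as read.
2. For the 15-letter endpoint, count a post-reference visit as not a success under NRI when fewer than 20 letters were read at 4 m and no 1 m test was done. The exception is an eye that already shows a loss of 15 or more with the full 30-letter credit: it stays classified as an observed worsening.
3. For logMAR, do not set the value to missing and apply LOCF. Keep the observed 4 m count and present two values side by side, one with 30 letters at 1 m and one with 0. Where finger counting or hand movements was recorded, use that value.
4. Apply the same two bounds when the reference visit (Baseline or Week 8) lacks the 1 m test.
5. Report the number of affected eyes at each visit.

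The cost is a paragraph of SAP text and a few program lines. The figures will be slightly less favourable, and the rule in item 2 is conservative, since some eyes that had not in fact lost 15 letters will be counted as non-successes.

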## **7.2 Uveitis History**

Variables to be summarized will include:

- Duration of uveitis (months) at baseline of Study M11-327
- Type of uveitis (intermediate, posterior, intermediate + posterior, panuveitis) at baseline of the parent study, Study M10-877/M10-880
- Diagnosis (idiopathic, birdshot choroidopathy, multifocal choroiditis and panuveitis, Vogt Koyanagi Harada, sarcoid, Behcet's, Other) at baseline of the parent study, Study M10-877/M10-880

## **7.3 Medical History**

Medical history data at baseline of the parent study, Study M10-877/M10-880, will be summarized and presented using body systems and conditions/diagnoses. The body systems will be presented in alphabetical order and the conditions/diagnoses will be presented in alphabetical order within each body system. The number and percentage of subjects with a particular condition/diagnosis will be summarized. Subjects reporting more than one condition/diagnosis within a body system will be counted only once for that body system.

## **7.4 Prior Medications**

Prior uveitis medications are defined as any uveitis-related medication discontinued prior to the first dose of study drug in the parent study, Study M10-877/M10-880. Prior uveitis medication will be summarized by generic drug name. In addition, the following

therapies discontinued prior to the first dose of study drug in the parent study, Study M10-877/M10-880 will be summarized by counts and percentages:

- Immunosuppressants
  - Azathioprine
  - Cyclosporine
  - Methotrexate (MTX)
  - Mycophenolate mofetil or equivalent drug (e.g., mycophenolic acid)
  - Tacrolimus
- Corticosteroids
  - Oral corticosteroids
  - Topical corticosteroids
  - Other corticosteroids

Previous medication is defined as any medication taken prior to the first dose of adalimumab in Study M11-327. The number and percentage of subjects who had taken previous medications will be summarized by generic drug name based on the World Health Organization (WHO) drug dictionary.

## **7.5 Concomitant Medications**

Medications with a start date prior to or on the first dose of adalimumab in Study M11-327 and a stop date on or after the first dose of adalimumab in Study M11-327 or a missing stop date will be considered as concomitant medications at baseline of Study M11-327. If the start date is missing and the stop date is on or after the baseline date in Study M11-327, or if start and stop dates are both missing, the medication will also be considered as concomitant at baseline in Study M11-327. The following therapies used by subjects at baseline in Study M11-327 will be summarized by counts and percentages:

- Immunosuppressants (IMMs)
  - Azathioprine

- Cyclosporine
- Methotrexate (MTX)
- Mycophenolate mofetil or equivalent drug (e.g. mycophenolic acid)
- Tacrolimus
- Corticosteroids (CSs)
  - Oral corticosteroids
  - Topical corticosteroids
  - Other corticosteroids

Concomitant medication is defined as any medication that started prior to the first dose of adalimumab in Study M11-327 and continued to be taken after the first dose of adalimumab in Study M11-327 or any medication that started after the first dose of adalimumab in Study M11-327, but not after the last dose of adalimumab in Study M11-327. The number and percentage of subjects who had taken concomitant medications will be summarized by generic drug name based on the World Health Organization (WHO) drug dictionary.

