5.0 Investigational Plan

5.1 Overall Study Design and Plan: Description

This study is a Phase 3, open-label multicenter study designed to evaluate long-term safety and efficacy of adalimumab in adult subjects with non-infectious intermediate-, posterior-, or pan-uveitis who have either discontinued from Study M10-877 or Study M10-880 for having met "Treatment Failure" criteria or have successfully completed Study M10-877 or Study M10-880. Subjects who prematurely discontinue from Study M10-877 or Study M10-880 for reasons other than for Treatment Failure as defined in the parent protocol, will not be eligible for this study.

Figure 1. Study Schematic

* Visits will occur every 12 weeks following Week 66 until the end of the study (not to exceed 15 March 2018).

Subjects rolling over from Study M10-877 and Study M10-880 will be evaluated for entry into this study at the final or last visit in the parent study. Therefore, Study M11-327 Baseline (Week 0) visit will be performed on the same day as the Final/Early Termination visit in the parent studies. At this visit, after administering and obtaining the subject's consent, subjects will be evaluated to ensure they meet all inclusion criteria and none of the exclusion criteria listed in Section 5.2. If the Baseline visit occurs greater than (>) 14 days after the Final/Early Termination visit of the parent study, all procedures listed in the Baseline visit must be completed. The maximum amount of time allowed between the Final/Early Termination visit of the parent study and the Baseline visit of Study M11-327 is 28 days.

Starting at Baseline, all subjects will receive open-label adalimumab 40 mg dose eow SC regardless of treatment assignment in the randomized, double-masked Study M10-877 or Study M10-880.

As subjects who discontinue from Study M10-877 or Study M10-880 due to "Treatment Failure" will have active disease on study entry into Study M11-327, concomitant therapy with corticosteroids (oral or topical) and/or any one of the immunosuppressive therapies permitted in Study M10-877 and Study M10-880, will be allowed as necessary to control intraocular inflammation.

Subjects who successfully complete Study M10-877 or Study M10-880 and have inactive disease at time of entry into Study M11-327 may continue, taper and/or discontinue concomitant corticosteroids and/or immunosuppressive therapy which were permitted in Study M10-877 and Study M10-880 based on the investigator's clinical judgment.

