## **6.0 Analysis Conventions**

### **6.1 Definition of Baseline and Final Observation**

Baseline of the parent study, Study M10-877/M10-880, is defined as the last non-missing observation made on or prior to the first dose of study drug in Study M10-877/M10-880.

Baseline of Study M11-327 is defined as the last non-missing observation made on or prior to the first dose of study drug in Study M11-327.

The final observation is defined as the last non-missing observation available prior to last dose plus 70 days.

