- Change in dose of IMM at each study time point relative to baseline for subjects who had inactive uveitis when they entered the study and to Week 8 for subjects who had active uveitis when they entered the study only in subjects on IMMs at baseline/Week 8 of Study M11-327.
- Proportion of subjects who started systemic CS in Study M11-327.
- Systemic CS dose at each study time point.
- Proportion of subjects at each study time point with

- Systemic CS dose = 0 mg/day
- Systemic CS dose > 0 to  $\leq$  5 mg/day
- Systemic CS dose > 5 to  $\leq$  7.5 mg/day
- Systemic CS dose > 7.5 to  $\leq$  10 mg/day
- Systemic CS dose > 10 to  $\leq$  20 mg/day
- Systemic CS dose > 20 mg/day
- Percent change in systemic CS dose at each study time point relative to baseline only in subjects on CS at baseline.
- Proportion of subjects in steroid-free quiescence at each study time point.
- Proportion of subjects in quiescence and for subjects without quiescence the proportion of subjects
  - with/without a change in concomitant medication (topical/systemic corticosteroids, immunosuppressants) within 5 days after non-quiescence and with/without quiescence at the next visit (at least 8 Weeks after non-quiescence)
  - with premature discontinuation
- OCT evidence of macular edema in at least one eye at each study time point.
- Central retinal thickness left/right eye and mean of both eyes at each study time point by OCT machine.
- Percent change in central retinal thickness (1 mm subfield) in each eye at each study time point relative to Baseline for subjects who had inactive uveitis when they entered the study and to Week 8 for subjects who had active uveitis when they entered the study.
- Change in NEI Visual Functioning Questionnaire (VFQ-25) score at each study time point relative to Baseline for subjects who had inactive uveitis when they entered the study and to Week 8 for subjects who had active uveitis when they entered the study.

For analysis of central retinal thickness, the central retinal thickness measured by the investigator will be used. Changes and percent changes in central retinal thickness may only be calculated for measurements from the same machine. Central retinal thickness

will be analyzed excluding patients with macular hole and/or rhegmatogenous retinal detachment affecting the macular.

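### Steroids and immunosuppressants started on the first-dose day count as baseline use but not as concomitant medication, and can set the reference for percent change in steroid dose in active entrants

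*SAP*

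**What the plan says.** SAP 7.5 has two rules. For the table of therapies in use at baseline it takes "Medications with a start date prior to or on the first dose of adalimumab in Study M11-327", with a stop date on or after that dose or no stop date. For the general summary by generic name it has two limbs. The first is "any medication that started prior to the first dose of adalimumab in Study M11-327 and continued to be taken after the first dose". The second is "any medication that started after the first dose of adalimumab in Study M11-327, but not after the last dose". SAP 7.4 adds: "Previous medication is defined as any medication taken prior to the first dose of adalimumab in Study M11-327".

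For measurements generally, SAP 6.1 sets the M11-327 baseline as the "last non-missing observation made on or prior to the first dose of study drug in Study M11-327", and the Week 0 window in SAP 6.2 closes on Rx Day 1.

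Among the steroid variables, SAP 10.2 lists "Percent change in systemic CS dose at each study time point relative to baseline only in subjects on CS at baseline". No other reference is given for subjects who entered with active uveitis. In the same list, change in immunosuppressant (IMM) dose and the 50% reduction in immunosuppression load are both measured from Week 8 in those subjects.

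Protocol 5.1 states that the "Study M11-327 Baseline (Week 0) visit will be performed on the same day as the Final/Early Termination visit in the parent studies". Treatment Failure entrants have active disease on that day, and corticosteroids (CS), one immunosuppressant, or both are permitted to control it. Open-label adalimumab also starts at Baseline.

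**The concern.** The design makes it likely that some Treatment Failure entrants have CS or an immunosuppressant started or raised on the date of their first M11-327 dose. Two things follow.

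First, the two rules in SAP 7.5 do not fit together. A drug begun on that date is in use at baseline under one rule and is not concomitant under the other, although the subject takes it alongside adalimumab. The generic-name summary would miss it. If SAP 11.1 uses the same definition for its subgroup of concomitant corticosteroid use (yes/no), a subject whose only course began on Day 1 would be placed in the 'no' group. Safety is the primary objective, so that classification matters.

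Second, percent change in systemic CS dose could be measured from a dose given to control the entry flare. Reducing that dose as the flare settles would then appear as steroid reduction on adalimumab, when it may only be a return towards the earlier regimen.

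**Working it through.** **Step 1: apply the date rules.** Day 1 is the date of the first M11-327 dose, and there is no Day 0 (SAP 6.2). Protocol 5.2.3.2 lists start and end dates for medication but no clock times, so order within Day 1 cannot be recovered. The rules as date inequalities are:

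- Baseline use (7.5): start ≤ Day 1, and stop ≥ Day 1 or missing.
- Concomitant (7.5): start < Day 1 and continuing after Day 1; or start > Day 1 and not after the last dose.
- Previous (7.4): taken before Day 1.

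| Medication record | Baseline use | Concomitant | Previous |
|---|---|---|---|
| Start Day -1, ongoing | yes | yes | yes |
| Start Day 1, ongoing | yes | **no** | no |
| Start Day 1, stop Day 60 | yes | **no** | no |
| Start Day 2, ongoing | no | yes | no |
| Start Day -10, stop Day 1 | yes | **no** | yes |

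The same drug is concomitant if begun a day earlier or a day later, but not if begun on Day 1. This follows from the wording and needs no assumption about how often it happens.

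When a dose is changed on Day 1, the old record (stop Day 1) and the new one (start Day 1) both satisfy the baseline rule. The SAP gives no tie-break.

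**Step 2: references for active entrants in SAP 10.2.**

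| Variable | Reference in active entrants |
|---|---|
| 50% reduction in immunosuppression load (includes prednisone) | Week 8 |
| Change in IMM dose | Week 8 |
| Percent change in systemic CS dose | Baseline |
| CS dose by visit, dose categories, steroid-free quiescence | none needed |

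Only percent change in CS dose is tied to entry. SAP 10.2 does not say how the baseline dose is derived and does not refer to 7.5. The rule in 6.1, which includes the day of the first dose, is the only baseline definition available. It makes a Day 1 dose the natural reference.

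**Step 3: what the reference does to the result.** Percent change = (later dose - reference dose) / reference dose. The doses below are assumed for illustration: 40 mg/day started on Day 1, and 10 mg/day at a later visit.

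- From the Day 1 dose: (10 - 40)/40 = -75%.
- From an earlier 5 mg/day: (10 - 5)/5 = +100%, or +5 mg/day.
- From an earlier 0 mg/day: percent change is undefined; the absolute change is 10 - 0 = +10 mg/day. This subject would enter the percent-change denominator only because of the Day 1 start.

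In relative terms, a later dose of 0.5, 0.25 or 0.1 of the Day 1 dose is reported as -50%, -75% or -90%. If the earlier dose was 0.25 of the Day 1 dose, the same later doses are +100%, 0% and -60% from it.

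**Step 4: size across the study.** This depends on the fraction of active entrants whose CS was started or raised on Day 1. The documents do not give it. At 0% there is no effect; at 50%, half of the active stratum would carry a Day 1 dose as its reference.

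**The case against.** The strongest reply concerns the steroid result. SAP 7.5 defines a table of counts and percentages, not a dose. SAP 10.2 does not cite it. Footnote a to Protocol Table 1 has the Baseline activities completed at the parent final visit and used in the M11-327 analysis, and Protocol 5.3.1.1 transfers therapy ongoing at that visit to the M11-327 eCRF. A programmer could therefore take the regimen ongoing at failure as baseline. This stands as a limit: the effect on percent change is the natural consequence of 6.1, not an instruction in the text.

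The reach is also narrow. A reader might infer that the steroid-sparing results of active entrants as a whole start from a treatment-induced peak. They do not: immunosuppression load and IMM dose change use Week 8, and CS dose by visit, the dose categories and steroid-free quiescence need no reference. Nor is therapy added at entry hidden. The listed CS and IMM classes appear in the baseline table, split by active and inactive uveitis, and CS dose is shown from Week 0.

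Two further inferences are tempting. One is that a Day 1 starter would be reported as not having started CS. SAP 10.2 says only that CS was started in M11-327, and nothing prevents a subject from counting both there and at baseline; the rule is missing rather than wrong. The other is that a Day 1 change from 10 to 40 mg would give a 50 mg baseline. SAP 7.5 classifies use and never sums doses, so this is only a possible programming outcome.

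Finally, all efficacy analyses are descriptive. That lowers the stakes but does not make a mislabelled change correct.

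**Conclusion.** The gap in SAP 7.5 is established from the wording: Day 1 starts are baseline use but not concomitant medication. Their loss from the generic-name summary follows directly. Their loss from the concomitant-corticosteroid subgroup in SAP 11.1 follows only if that subgroup uses the 7.5 definition, which the SAP does not state.

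The steroid point holds in a limited form. One variable, percent change in systemic CS dose in active entrants, can take a Day 1 flare dose as its reference, and its taper would then be reported as steroid reduction. This assumes that 6.1 governs the baseline dose and that some subjects had CS started or raised on Day 1. For an affected subject the sign of the result can change, as in the illustration. The effect on the stratum cannot be computed and may be nil. How a start on Day 1 is counted for the proportions starting CS or IMMs, and which record gives the dose when it changes that day, is undefined.

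**What to change.** 1. In SAP 7.5, change the second limb of the concomitant definition to 'started on or after the first dose', and state whether SAP 11.1 uses that definition.
2. In SAP 10.2, count CS and IMM starts dated on or after Day 1 as started in Study M11-327. Where a dose changes on Day 1, do not sum the old and new records, and say which one gives the baseline dose.
3. For active entrants, keep the change from baseline and add one or both of: change in CS dose from the regimen in force before the parent Final/Early Termination visit, in mg/day so that subjects at 0 mg are kept; and change from Week 8, as for the IMM variables.

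Anchoring on the day before the first dose would not be enough. Protocol 5.1 allows up to 28 days between the parent final visit and Baseline, and therapy begun in that gap would still be the reference. It would also leave percent change undefined for subjects at 0 mg.

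The cost is SAP wording and a derivation from dates and doses already collected. Therapy ongoing at the parent final visit is transferred to the M11-327 eCRF; a regimen closed before then would come from the parent-study data. The steroid-reduction figure for active entrants may look less favourable.
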